The participants will be instructed to complete the 8 self-administered instruments, including PROMIS-Sleep Disturbance, PSQI, PROMIS-Fatigue, PROMIS-depression, CES-D, EORTC QLQ-C30, PROMIS-Physical Function, and PSS on the day of posttest data collection. They will be asked to return the completed instruments on their sleep lab visit.

Post-treatment data collection: The post-treatment data collection will start on the next day after completion of the 14-day intervention protocol. Following the same protocol described in baseline data collection, the participants will report to the sleep laboratory 7 pm and then complete the MoCA and the NIH Toolbox Cognition Battery, administered by a research staff.

Before going to bed, the participants will be connected to the PSG recording at their regular bedtime hours and undergo overnight PSG monitoring. With the assistant from a research staff, the participant will self-insert the thermistor just before going to bed and will remove thermistor after final awakening in the morning. The PSG and core temperature recordings for the analysis will start at the time of lights out and will end after final awakening in the morning. During the post-treatment data collection, the participants will complete the daily log before going to bed and the following morning.

Before checking out of the sleep laboratory, the participant will return the daily log. All participants will receive an exit interview before checking out the sleep lab or within 3 days regarding issues or difficulties encountered during the study and complete a list of rating scales measuring levels of burden for study activities.

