The objective of **Aim 3** is to assess the effects of bright light on circadian rhythms. Circadian rhythm will be measured by nocturnal core body temperature before and after the light intervention. The phase shift of the nocturnal core body temperature will be calculated by the timing of the peak and trough of the temperature curve. To take full advantage of the availability of intensive data from continuous sleep-time core body temperature measurement, the difference in circadian rhythms between groups will also be compared using functional data analysis (FDA), a collection of emerging techniques about the analysis of information on curves or functions. Unlike the conventional methods such as ANOVA that only focus on the differences at a few fixed time points, FDA provides information about curves, surfaces, or anything else varying over a continuum. Specifically, after a proper registration or alignment of the temperature curves from each individual, FDA will allow us not only to compare the overall circadian rhythms between groups, but also correlate the curves with other measured data such as symptom scores from Aim 2. Such a curve-based analysis will allow us to compare not only the magnitude (peak and trough) but also the shift in the circadian cycle.

Mediation analysis will also be performed to better understand the possible mechanism of bright light intervention on the 4 symptoms. Specifically, functional principal component analysis (FPCA) will first be applied to core body temperature during pre- and post-treatment periods separately to identify distinct patterns of circadian rhythms. The causal-step approach outlined in the classic work of mediation analysis will then be used to estimate the direct and indirect treatment effects and to quantify the potential mediating effects of circadian rhythms. Due to relatively small sample size, the interest will focus more on the estimation and precision of mediating effects rather than significance testing.

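### The Aim 3 mediation analysis aims at precision but names causal steps, which give no interval for the indirect effect, and its mediator may lose circadian phase

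*SAP*

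**What the plan says.** **Method and aim (SAP, Aim 3, mediation paragraph).** The first step derives the mediator: "functional principal component analysis (FPCA) will first be applied to core body temperature during pre- and post-treatment periods separately". Then comes the method: "The causal-step approach outlined in the classic work of mediation analysis will then be used to estimate the direct and indirect treatment effects". The paragraph closes with its aim: "Due to relatively small sample size, the interest will focus more on the estimation and precision of mediating effects rather than significance testing".

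It names no standard error or interval for the indirect effect. It does not say which score is the mediator (pre, post or change) or how many components are kept. The Protocol has no statistical text that fills these gaps.

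**Curves (SAP, Aim 3, functional data analysis).** The group comparison of temperature curves is made "after a proper registration or alignment of the temperature curves from each individual". The mediation paragraph does not say whether its FPCA uses the registered or the raw curves.

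**Time origin (Protocol).** Under baseline data collection, the temperature data analysed are 5-minute readings from lights out. Under post-treatment data collection: "The PSG and core temperature recordings for the analysis will start at the time of lights out".

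**Order of measurement (Protocol, post-treatment).** Participants complete the self-report forms, the list ending "PROMIS-Physical Function, and PSS on the day of posttest data collection". For cognition, "the participants will report to the sleep laboratory 7 pm and then complete the MoCA and the NIH Toolbox Cognition Battery". Both come before that night's temperature recording.

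**The concern.** The stated goal and the named method do not match. Causal steps ask in turn whether the total effect, the path from treatment to mediator and the path from mediator to outcome are significant. They answer yes or no. A small study that wants to show how well it has measured mediation needs an interval, and that is the one thing the plan does not provide.

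The second issue is what the mediator contains. Bright light may act by moving circadian phase, and Aim 3 measures phase shift. If the curves entering the FPCA have been aligned, or if their time origin (lights out) moves with the person's phase, the scores carry little or no phase. An indirect effect carried by phase would then be estimated as small or absent, and the report could wrongly conclude that light does not work through the circadian system.

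**Working it through.** The plan gives no sample size, effect size or standard deviation, so there is no figure to reproduce. Everything below rests on assumed inputs at 15/20/30 per arm.

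**1. The point estimate is available.** Let a be the effect of treatment on the mediator, b the effect of the mediator on the symptom given treatment, c the total effect and c' the direct effect. In linear models with the same covariates, c - c' = a × b. With a = 0.8 and b = 0.5 (unit residual SDs), a × b = 0.40. Without any gate, the simulated mean estimate was 0.40 (40,000 replicates per cell).

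**2. The missing precision.** Approximate variance of the estimate: b² × SE(a)² + a² × SE(b)². At 20 per arm, SE(a)² = 2/20 = 0.100 and SE(b)² ≈ 1/38 = 0.026. The variance is 0.25 × 0.100 + 0.64 × 0.026 = 0.042, the SE is 0.20, and the 95% width is 2 × 1.96 × 0.20 ≈ 0.8. Simulated Monte Carlo intervals had mean width 1.02/0.85/0.68 at 15/20/30 per arm. At 20 per arm the interval is about twice as wide as the effect, and the plan as written would not show this.

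**3. Choice of interval (mediator observed directly).** The normal-theory interval covered 90-93%, with misses mostly on one side (truth above it in 6-10%, below it in under 1%). The percentile bootstrap covered 93-94% (4-6% and 1-2%).

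**4. What would follow if the steps were used as a gate.** The plan does not state this. All three tests at two-sided 5%, a = 0.8, b = 0.5:

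| Direct effect c' | All steps pass, 15/20/30 per arm | Mean of passing estimates ÷ truth |
|---|---|---|
| 0 | 8/14/25% | 1.63/1.40/1.20 |
| 0.4 | 22/39/67% | 1.59/1.35/1.13 |
| 0.8 | 34/54/81% | 1.57/1.33/1.12 |

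The a and b tests alone pass in about 38/57/82%. Hand check of the total-effect step at 20 per arm with c' = 0: c = 0.40, residual variance 1 + 0.5² = 1.25, SE = √(1.25 × 2/20) = 0.354, ratio 1.13 against a critical value of about 2.02. It passes in roughly 19%, consistent with the simulated failure rate of 80%.

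**5. Does the mediator keep phase?** Assumed model: 8-hour curves on a 5-minute grid, 24-hour cosine, trough 4 h after lights out, phase SD 1.0 or 1.5 h, effect carried by phase, true indirect effect 0.40. Baseline-adjusted regressions, first two FPCA scores except in the last row:

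| Curves or score used | Mean estimate |
|---|---|
| Unregistered, lights-out independent of phase | 0.29-0.33 |
| Unregistered, lights-out follows 50% of phase (20 per arm) | 0.23-0.31 |
| Unregistered, follows 80% (20 per arm) | 0.06-0.14 |
| Unregistered, follows 100% (20 per arm) | about 0 |
| All curves shifted to a common trough | -0.01 to 0.01 |
| Cruder alignment holding end values constant | 0.02-0.04 (1.0 h), 0.13-0.16 (1.5 h) |
| Clock-time trough score, bedtime moving with phase (20 per arm) | 0.27-0.32 |

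Leaving the curves unregistered is therefore not enough; the clock time must also be kept.

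**6. Bootstrap with the FPCA re-run in each resample (lights-out independent of phase).** With two scores, coverage of 0.40 was 95/92/92% (1.5 h) and 93/91/89% (1.0 h). Coverage of the estimator's own mean was 95-99%, so the shortfall comes mainly from shrinkage by imperfect scores. Separate and pooled FPCA gave means within 0.003 of each other.

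**The case against.** The strongest reply is that the SAP already disowns the test-based use: it applies the regressions to estimate effects and plays down testing. That stands. A reader might infer from the label that mediation will be declared only when every step is significant. The documents state no such rule, so the pass rates and inflation in step 4 describe a conditional harm and should not carry the weight of the point. What survives is that no interval is named anywhere.

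A reader might also infer that the plan aligns the curves at the trough and so discards phase. The documents do not support that. Registration is mentioned for the curve comparison, no landmark is given, and the SAP says the shift in the cycle will be compared as well as its magnitude. The near-zero result under trough alignment follows almost by construction. The silence about the mediation FPCA remains, and the lights-out origin is in the Protocol whatever the registration.

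Finally, a reader might infer from the order of measurement that cause and effect are reversed. That goes too far. Phase after 14 days of light is a state that one night samples, PSG comes from the same night, and the daily log (sleep/wake activities and fatigue) is also completed the next morning. A stated limitation is enough.

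**Conclusion.** The point holds in a limited form. The SAP wants precision for the mediating effect and names a method that does not supply it. The point estimate from the same regressions is sound when no gate is applied. Separately, the mediator is not tied down, and an effect carried by phase could be partly or wholly lost if the curves are aligned or if bedtime moves with phase.

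The size cannot be fixed from the documents. Under the assumed inputs at 20 per arm, the unreported interval is about 0.85 wide around an effect of 0.40. When lights-out follows 80% of phase, only 0.06/0.40 = 15% to 0.14/0.40 = 35% of the effect is recovered. These figures depend on the assumed paths, the cosine model and the degree of tracking.

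The change should be made, but its reach is the Aim 3 mechanism analysis. Aims 1 and 2 are unaffected.

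**What to change.** Replace the causal-step sentence with the following:

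- **Mediator set, fixed in advance.** For example, the first two FPCA scores plus the trough time that Aim 3 already derives, expressed as clock time and not as time since lights out. This keeps phase whatever the registration or lights-out time.
- **Models.** Regress each post-treatment mediator score on group and baseline mediator scores. Regress the post-treatment symptom on group, post-treatment mediator scores, baseline mediator scores and baseline symptom.
- **Estimates.** Report the direct effect and the total indirect effect (the sum of a × b over the mediators) with percentile-bootstrap 95% intervals, re-running the FPCA in each resample, whatever any test shows. The total does not depend on the sign or order of components. Define it as the product: c - c' is identical only when both models share the same covariates, and here the mediator model omits the baseline symptom.
- **Limitations to state.** Post-treatment questionnaires and cognition tests precede that night's temperature recording; imperfect scores shrink the indirect effect; coverage may fall somewhat below 95%.

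A pooled FPCA basis is needed only if pre and post scores are to be differenced or compared.

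The cost is a few sentences and some computing, with no new data. Each added score widens the interval: median width 1.37/0.98/0.70 with three FPCA scores against 1.10/0.84/0.63 with two, at 15/20/30 per arm. The set suggested here (two scores plus trough time) was not simulated as a whole, so the three-score widths are only a guide.

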**Effects of Bright Light on Co-occurring Cancer-related Symptoms
in Breast Cancer Survivors**

NCT03304587

PI: [name]

Statistical Analysis Plan

May 1, 2022

Statistical Analysis Plan

The data analysis of **Aim 1** will be descriptive in nature. To assess the feasibility of the proposed study protocol, the numbers of subjects contacted and screened, the proportion of eligible subjects from those contacted, the proportion of those successfully recruited from the pool of eligible subjects, the proportion retained of those recruited, completeness of the data collected, ease of using each measure, and adverse effects (if there are any) will be described using summary statistics. Adherence to treatment will be assessed by measuring timing of visor cap usage. Adherence to outcome reporting will be evaluated by estimating completion rates of scheduled PSG recordings, core body temperature measures, and self-report forms at both time periods. The proportion and the reason for missing data on each outcome will also be assessed.

The objective of **Aim 2** is to assess the effects of bright light on the 4 symptoms (sleep disturbance, fatigue, depression, cognitive dysfunction) and quality of life. Nocturnal sleep patterns will be measured objectively and subjectively. Objective sleep patterns will be monitored in a sleep laboratory by all-night PSG before and after the light intervention. The endpoints for sleep patterns (the sleep continuity measures include sleep onset latency, arousals, wake after sleep onset, and sleep efficiency) will be derived from scoring the PSG record by a polysomnographer blind to intervention assignment. Subjective endpoints for sleep patterns (sleep onset latency, sleep disturbance, and sleep efficiency) will be self-reported by participants before and after the light intervention. For each endpoint, the between-group difference will be compared using two-way ANOVA for repeated measurement data and to account for potential correlation among multiple measurements taken from the same individual. Important covariates such as ambient light and the level of stress (as measured by PSS) will be adjusted if necessary. Fatigue, depression, cognition, and quality of life will be subjectively and objectively assessed before and after the light intervention. Between-group differences in those subjective measurements will be compared using two-way ANOVA.

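### The mediation analysis specifies no baseline rhythm or baseline symptom terms, so a pre-existing link between the two can pass for an indirect effect when light shifts the rhythm

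*SAP*

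**What the plan says.** The mediation paragraph closes the SAP, under Aim 3. Its first step is that "functional principal component analysis (FPCA) will first be applied to core body temperature during pre- and post-treatment periods separately". Its second is that "The causal-step approach outlined in the classic work of mediation analysis will then be used to estimate the direct and indirect treatment effects". No mediator or outcome equation is written. The text does not say whether the mediator is a post-treatment score or a change, and it lists no covariates. On purpose, it says that "the interest will focus more on the estimation and precision of mediating effects rather than significance testing".

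The baseline data exist. Under Aim 3, "Circadian rhythm will be measured by nocturnal core body temperature before and after the light intervention". Under Aim 2, "Fatigue, depression, cognition, and quality of life will be subjectively and objectively assessed before and after the light intervention", and sleep is also measured at both times. The study schedule in the Protocol (Procedures) agrees.

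The SAP's only covariate sentence is under Aim 2: "Important covariates such as ambient light and the level of stress (as measured by PSS) will be adjusted if necessary". It names neither baseline rhythm nor baseline symptom and is not extended to Aim 3. The functional data analysis paragraph also plans to "correlate the curves with other measured data such as symptom scores from Aim 2", again without stating any adjustment.

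**The concern.** The indirect effect is the product of two paths: group to rhythm (a) and rhythm to symptom given group (b). Assignment can protect the first. It cannot protect the second, because nobody assigns the rhythm.

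Suppose women with a poorer temperature rhythm were already more fatigued at baseline, and both features persist over a two-week treatment. Rhythm and fatigue will then be correlated within each group afterwards, even if changing the rhythm does nothing to fatigue. In their usual form the causal steps regress the mediator on treatment, then the outcome on treatment and mediator. Applied that way, they read this correlation as the b path.

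The SAP makes estimation the purpose of the analysis, so a bias in favour of the hypothesised mechanism damages its main product. The Aim 2 group comparisons are not affected. The planned curve-symptom correlations are exposed to the same confounding. If group is left out, they also pick up any group difference that moves both variables.

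**Working it through.** **Inputs.** The documents give no effect sizes, SDs or correlations. On sample size they say only "Due to relatively small sample size". There is no stated figure to reproduce, and every value below is an assumption in SD units:

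- 20 women per group, balanced at baseline
- light moves the rhythm by a = 0.8 and the symptom by 0.5
- true mediator effect zero
- baseline rhythm-symptom correlation r0 = 0.2 to 0.5
- pre/post stability s = 0.5 to 0.7 for both variables

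**Model A: the measured baselines carry the link.** Post rhythm = s × baseline rhythm + a × group + error. Post symptom = s × baseline symptom + 0.5 × group + error. Within groups, the expected slopes and indirect effects are:

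- no baseline terms: b = r0 × s², indirect = a × r0 × s²
- both baselines in both models: b = 0, indirect = 0
- change scores: b = r0 × (1 − s) / 2

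| r0 | s | No baseline terms | Both baselines | Change scores |
|---|---|---|---|---|
| 0.2 | 0.5 | 0.8 × 0.050 = 0.040 | 0 | 0.8 × 0.050 = 0.040 |
| 0.2 | 0.7 | 0.8 × 0.098 = 0.078 | 0 | 0.8 × 0.030 = 0.024 |
| 0.5 | 0.5 | 0.8 × 0.125 = 0.100 | 0 | 0.8 × 0.125 = 0.100 |
| 0.5 | 0.7 | 0.8 × 0.245 = 0.196 | 0 | 0.8 × 0.075 = 0.060 |

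Against a total effect of 0.5 SD, the range without baseline terms is 0.04/0.5 = 8% to 0.196/0.5 = 39% falsely mediated. Simulation (4,000 trials per setting) gave means within 0.005 of these values. The SD of the estimate was 0.14 to 0.16 without baseline terms and about 0.145 with them, so adjustment does not cost precision. A separate run with 10 per group (a = 0.5, r0 = 0.4, s = 0.7) gave SDs of 0.19 without and 0.16 with baseline terms.

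**Model B: each measurement is a noisy reading of a stable trait.** All rhythm-symptom correlations equal r0, and each variable correlates s with itself over time. Then:

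- no baseline terms: b = r0
- both baselines: b = r0 × (1 − s) / (1 + s − 2 × r0²)
- change scores: b = 0

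| r0 | s | No baseline terms | Both baselines | Change scores |
|---|---|---|---|---|
| 0.2 | 0.5 | 0.16 | 0.8 × 0.070 = 0.056 | 0 |
| 0.2 | 0.7 | 0.16 | 0.8 × 0.037 = 0.030 | 0 |
| 0.5 | 0.5 | 0.40 | 0.8 × 0.250 = 0.200 | 0 |
| 0.5 | 0.7 | 0.40 | 0.8 × 0.125 = 0.100 | 0 |

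Here adjustment removes between 1 − 0.200/0.40 = 50% and 1 − 0.030/0.16 = 81% of the bias. Simulation agreed to within 0.01.

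**No light effect on the rhythm.** With a = 0 and balanced groups, the product averages zero in both models, however biased b is. It is noisier without the baseline terms: in Model A at r0 = 0.5, s = 0.7, the SD is 0.093 without and 0.040 with them.

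**The case against.** The strongest reply is that the SAP leaves the models unwritten. Pre-treatment curves go through FPCA as part of the mediation work, so baseline adjustment or change scores may be intended, and naming the causal steps does not rule out covariates. This stands in part. A reader might infer that the regressions exclude baseline terms; the text supports only that it specifies none. But it gives the pre-treatment scores no role, and nothing elsewhere in the SAP or Protocol supplies one.

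Two other strong readings also go too far:

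- **That a spurious indirect effect always appears.** It needs the groups to differ on the post-treatment rhythm. If light does not move the rhythm and the groups are balanced, the expected value is zero.
- **That adding baselines cures the problem.** This is true in Model A, but not in Model B. Each temperature curve comes from a single night, so measurement noise is plausible.

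The separate FPCA also complicates the remedy. Pre and post analyses can yield different component functions, so a baseline score may not measure the same feature as the post score.

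Finally, this is a third-aim analysis with an acknowledged small sample and little emphasis on testing. That limits the stakes. It does not excuse a bias in the estimate, since estimation is the stated interest.

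**Conclusion.** The concern holds as an omission with a predictable direction. The mediation analysis specifies no baseline mediator or baseline symptom terms, the data for both are collected, and assignment does not protect the path that needs them. When light shifts the rhythm or the groups differ on it, a pre-existing association is partly reported as mediation.

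Under Model A's assumptions the bias is about 0.04 to 0.20 SD. If the measurements are noisy readings of stable traits, it is larger: 0.16 to 0.40 SD unadjusted and 0.03 to 0.20 SD adjusted. At the low end, 0.04 SD is small beside a sampling SD of about 0.145. None of these inputs comes from the documents, so the ranges show plausible size and do not predict the result. The point merits correction because the remedy is cheap and uses data already scheduled.

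**What to change.** Amend the Aim 3 text in four places:

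1. **FPCA step.** Compute scores on a common basis, either by pooling pre and post curves or by projecting post curves on the baseline components, so that a woman's two scores describe the same feature.
2. **Mediation models.** State that the mediator model and the outcome model both include the baseline mediator score and the baseline value of the symptom.
3. **Curve-symptom association.** Include group and the same baseline terms.
4. **Sensitivity analysis.** Report a change-score version beside the adjusted one. In the working, each method is unbiased under the model where the other is not, so agreement is reassuring, and a gap shows how far the result depends on the assumption.

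The cost is SAP wording, a small change to the FPCA step and two degrees of freedom per model. With one component score and an assumed 40 women, residual degrees of freedom go from 40 − 3 = 37 to 40 − 5 = 35 in the outcome model, and from 40 − 2 = 38 to 40 − 4 = 36 in the mediator model. No new data are needed.
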